## LIST OF ABBREVIATIONS AND RELEVANT DEFINITIONS

ABR	General Assessment and Registration form (ABR form), the application form that is required for submission to the accredited Ethics Committee; in Dutch: Algemeen Beoordelings- en Registratieformulier (ABR-formulier)
CA	Competent Authority
CCMO	Central Committee on Research Involving Human Subjects; in Dutch: Centrale Commissie Mensgebonden Onderzoek
COPD	Chronic Obstructive Pulmonary Disease
CVD	Cardiovascular Diseases
CV	Curriculum Vitae
DM2	Diabetes Mellitus type 2
EU	European Union
GCP	Good Clinical Practice
GDM	Generic Disease Management
GDPR	General Data Protection Regulation; in Dutch: Algemene Verordening Gegevensbescherming (AVG)
IC	Informed Consent
NHG	Dutch College of General Practitioners
METC	Medical research ethics committee (MREC); in Dutch: medisch-ethische toetsingscommissie (METC)
Sponsor	The sponsor is the party that commissions the organisation or performance of the research, for example a pharmaceutical company, academic hospital, scientific organisation or investigator. A party that provides funding for a study but does not commission it is not regarded as the sponsor, but referred to as a subsidising party.
P3CEQ	Person Centred Coordinated Care Experiences Questionnaire
PROMIS	Patient-Reported Outcomes Measurement Information System GLOBAL -
GLOBAL10	10
SDM	Single Disease Management
WMO	Medical Research Involving Human Subjects Act; in Dutch: Wet Medisch-wetenschappelijk Onderzoek met Mensen

## SUMMARY

**Rationale:** Chronic diseases and multimorbidity are increasingly prevalent. However, over the last decades, attempts at improving primary care for chronic diseases have been focussed on the management of individual chronic diseases and single disease management (SDM) programs have been implemented in Dutch primary care. This causes multiple problems for patients with one or more chronic diseases, such as negative interaction between treatment of single diseases, high treatment burden, negative patient experiences, lack of attention for problems in other domains of life that may interact with the chronic disease, and difficulties in shared decision making by the use of strict protocols in SDM programs. A person-centred and holistic approach is widely recognized as the solution to the problems observed in chronic disease care. Therefore, we guided three large Dutch primary care cooperatives, who have been organizing SDM programmes on diabetes mellitus type 2 (DM2), COPD, and cardiovascular diseases (CVD) in primary care for the last decades, with the development of a new generic disease management (GDM) programme including a person-centered and holistic approach (CMO 2019-5756). The three primary care cooperatives have recently conducted a pilot study in which we evaluated the feasibility of the programme (CMO 2021-8106) to further optimise its content and procedures. In the coming years, all three primary care cooperatives will gradually implement the optimised programme in all general practices in their regions.

**Objective:** In the current study, our aim is to evaluate the effectiveness of the GDM programme on Quadruple Aim outcomes, i.e. patient experiences, population health, health care provider experiences, and cost effectiveness.

**Study design:** we will conduct a cluster randomized controlled trial in the three primary care cooperatives with a follow-up of 12 months. Fifteen practices will be randomised to either care as usual according to the current SDM programmes, or to the GDM programme including a person-centered and holistic care approach. Approximately 40 patients per practice with DM2, COPD and/or CVD will be recruited.

**Study population:** all patients with DM2, COPD and/or CVD who currently receive SDM according to the SDM programmes of the participating primary care cooperatives are eligible to participate.

**Intervention:** a GDM programme including person-centered and holistic care. This programme will replace the SDM programmes for DM2, COPD and CVD that are currently used in the participating primary care cooperatives.

**Main study parameters/endpoints:** effectiveness will be evaluated by Quadruple Aim outcomes at baseline, at 6 months, and at 12 months follow-up by comparing changes in the intervention group with the comparator group. Patient experiences will be measured with the P3CEQ questionnaire. Population health will be measured with the PROMIS Global-10 questionnaire. Self-management will be measured with the Patient Activation Measure (PAM) score. Healthcare professional experiences will be measured with the MASGZ and the COPILOT questionnaire. Data for calculating costs and conducting a cost-effectiveness analyses will be measured by the Medical Consumption questionnaire and the EQ-5D questionnaire and by process outcomes such as the number and type of consultations and referrals, and duration of consultations from the Electronical Medical Files. At 12 months, a purposive sample of patients and professionals will participate in focus group interviews to collect information on experiences and facilitators and barriers for further implementation. Also, the competences needed by the healthcare professionals to provide personalised and integrated chronic care will be explored.

**Nature and extent of the burden and risks associated with participation, benefit and group relatedness:**

- The intervention has been developed by the three primary care cooperatives in close collaboration with their healthcare professionals and their patient panels and with the guidance of our research group. Also, input from the Dutch College of General Practitioners (NHG) and from InEen, the branch organisation for primary care cooperatives, has been obtained to ensure that the intervention will suit their vision and future plans for reorganising Dutch primary care chronic disease management. The intervention is also in line with current movements in healthcare, such as the Positive Health concept.
- All three primary care cooperatives are intending to gradually implement the intervention throughout their regions in the upcoming years. Thus, the GDM programme will be implemented and will replace current SDM, even without the current cluster RCT as proposed in this study protocol.
- The burden and risks associated with the intervention are negligible and comparable with the usual care, i.e. the current SDM programmes.

- Patients in the control group will continue with their care as usual, i.e. single chronic disease management according to the protocols of the SMD programmes that have been used in the participating cooperatives since the last decade.
- The additional burden or risk associated with participation in this study is negligible. After written informed consent, patients in both groups will fill in a digital or paper questionnaire at baseline, 6 months, and 12 months. Estimated time to fill in the questionnaire is 20 minutes. A purposive sample of approximately 15 patients will participate in focus-groups interviews at the end of follow-up.

## 1. INTRODUCTION AND RATIONALE

Multimorbidity is increasingly prevalent. In 2016, 52% of the Dutch population had at least one chronic disease; 37% of Dutch population had two or more chronic diseases.[1] This increasing prevalence results in several problems. Multimorbidity is associated with poorer quality of life, functional health status and physical functioning, and higher mortality compared to patients with zero or one chronic condition.[2, 3] In addition, patients with multimorbidity have higher health care utilization than patients with one or no chronic disease; multimorbid patients had more contacts with general practice, more medication prescriptions, and more referrals to specialized care.[4, 5] Because of the impact of chronic diseases and the increasing number of patients with multimorbidity, costs of primary health care in the Netherlands are quickly rising. For instance, over the course of 2013 to 2016, the costs of primary care increased from 2.7 to 3.1 billion euros. This can largely be attributed to the increase in cost of care for people with chronic conditions.[6]

Over the last decade, attempts at improving primary care for chronic diseases have been focussed on the management of individual chronic diseases, with the implementation of single disease management (SDM) programs internationally. In the Netherlands, SDM programs have been widely implemented for diabetes mellitus type 2 (DM2), chronic obstructive pulmonary disease (COPD) and cardiovascular disease (CVD). The disease specificity of these programs causes 3 distinct problems for people with multimorbidity. First, the treatment of one disease according to a disease-specific guideline can interact negatively with the treatment or natural course of a co-existing disease.[7] The second problem is that the combination of various disease-specific guidelines leads to polypharmacy and increased treatment burden.[8] Last, because of the disease-specific fragmentation of primary care, people with multimorbidity are more likely to experience problems with coordination of care and lower quality of care.[9]

A patient centred and integrated care (PC-IC) approach is widely recognized as the solution to the problems in multimorbidity care.[7, 10, 11] Therefore, we guided three large Dutch primary care cooperatives, who have been organizing SDM programmes on DM2, COPD, and CVD in primary care for the last decades, with the development of a new generic disease management (GDM) programme including a person-centered, integrated, and holistic approach (CMO 2019-5756). The three primary care cooperatives have recently conducted a pilot study in which we evaluated the feasibility of the programme (CMO 2021-8106) to further optimise its content and procedures. In the coming years, all three primary care cooperatives will gradually implement the optimised programme in all general practices in their regions.

## OBJECTIVES

In the current study, our aim is to evaluate the effectiveness of the GDM programme on Quadruple Aim outcomes, i.e. patient experiences, population health, health care provider experiences, and cost effectiveness.

## 2. STUDY DESIGN

We will perform a cluster randomized controlled trial with a follow-up time of 12 months.

The three participating primary care cooperatives, i.e. Nijmegen, Arnhem, and Doetinchem, will recruit 15 general practices (clusters) who will be randomized using a 2:1 ratio in two study groups:

1. The intervention group: the GDM programme including a person-centered, integrated, and holistic approach
2. The control group: care as usual according the current SDM programmes

All practices will receive instructions from the research team on the procedures of the evaluation study. Participating practices will then start recruiting patients from a random sample of eligible patients, i.e. patients with DM2, COPD, or CVD who are currently receiving SDM. After written informed consent, information will be collected through questionnaires at baseline, 6 months and 12 months, and by interviews and data collection from electronic medical records. Information will also be collected from the participating healthcare providers through questionnaires and interviews.

In the two months prior to the start of the intervention, all practices in the intervention group will be trained in providing GDM by their own primary care cooperative. During follow-up two to three intervention meetings will take place including peer coaching and case study discussions.

Practices who are allocated to the usual care group will not receive any training, but will continue with their SDM programmes.

## STUDY POPULATION

### 2.1 Population

All patients who are currently enrolled in any of the SDM programmes for DM2, COPD, asthma or CVD are eligible for participation.

## 2.2 Inclusion criteria

- Currently enrolled in any of the SDM programmes for DM2, COPD, asthma or CVD.

## 2.3 Exclusion criteria

- Limited life expectancy (less than 3 months)
- Unable to speak or read the Dutch language

## 2.4 Sample size calculation

Due to the complexity of our intervention we will use two primary outcomes, i.e. health-related quality of life and patient experience of care. These outcomes are in line with the 2 patient-related aims of the Quadruple Aims concept. Patient-reported health-related quality of life will be measured using the 'PROMIS Global 10' questionnaire and the patient experience of care will be measured using the 'P3CEQ'. These questionnaires have been chosen after piloting several questionnaires in the preceding Phase2 of OPTIMA FORMA. Patients experienced these questionnaires as easy to complete and to understand.

The 'PROMIS global 10' assesses a person's health-related quality of life and consists of 10 questions. Two dimensions representing physical and mental health underlie the global health items in PROMIS. These global health scales, Global Physical Health (GPH) and Global Mental Health (GMH), can be used to efficiently summarize physical and mental health in patient-reported outcome studies.[12] The 10 global health items include ratings of the five core PROMIS domains with a response scale ranging from 1 to 5. The PROMIS global 10 is publicly available and has been widely used as outcome measure for quality of life in studies on different diseases.

The Person-Centred Coordinated Care Experience Questionnaire (P3CEQ) is a brief questionnaire that meets the requirements for a PREM that could assess the quality of care and guide quality improvement for people with (multiple) chronic conditions. It has been specifically designed to assess the experience of person-centred coordinated care, informed by a theoretical model that was developed to consider the relationship between care coordination, continuity and person-centred care. The P3CEQ was originally developed in the United Kingdom for persons with chronic conditions using primary care services.[13] Recently it has been translated and validated for the Dutch population.[14] It contains 14 items and the response scale ranges from 'never' (0), 'sometimes' (1), 'often' (2) and 'always' (3).

Because we value each aim (population health and patient experience) as equally important, we are using a composite primary outcome, which consist of the percentage of patients who have a clinically relevant improvement of at least the minimal clinically important difference (MCID), defined as  $0.5 \times \text{SD}$  of the baseline mean, in either the PROMIS GMH score OR the PROMIS GPH score OR the P3CEQ-score AND who experience no decrease of at least the MCID in either the PROMIS GMH score OR the PROMIS GPH score OR the P3CEQ-score.

In our recent pilot study [unpublished] we followed 98 patients who received our intervention for six months. Of the 79 patients who completed all questionnaires, we found that in 30.4% of the patients the requirements for a positive score on the composite primary outcome were met. Loss to follow-up was 20%. Based on these results and the longer duration of intervention in the evaluation study (12 months vs 6 months), we hypothesised that in the evaluation study 35% of the intervention patients compared to 20% of the usual care patients will improve more than  $0.5 \times$  the expected SD of baseline mean on one of the scores at 12 months, and show no decrease of the MCID on the other scores. We estimate that we need a total sample size of 680 patients (17 practices with an average of 40 patients per practice) to detect a difference of 15% between the control and intervention group, taken into account an alpha level of 5%, a power of 80%, an intra-class correlation coefficient (ICC) of 0.03 [15], and a loss to follow-up of 20%.

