#### 4.2 Randomisation, blinding and treatment allocation

The unit of randomisation will be the general practice (cluster). Practices will be randomised to intervention group (10 clusters) or comparator (5 clusters) in a 2:1 ratio. Five additional clusters will be randomised to the control group by a 2:1 ratio randomisation procedure in the parallel cluster RCT named EMBOSS in which the GDM programme will be adjusted to the needs of patients with low socioeconomic status (SES). In the EMBOSS cluster RCT the adjusted intervention will be provided to patients with low SES and at 12 months follow-up the effects will be compared to patients with low SES who have received care as usual. Figure 2 illustrates the combined randomisation procedure of both the OPTIMA FORMA and the EMBOSS cluster RCT.

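### Section 2.4 ties 80% power to 17 practices, but the design randomises 15 (10:5), or 20 (10:10) if the EMBOSS controls count, and the text does not say which; power is about 69-74% if they are excluded

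*Combined protocol and SAP*

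**What the plan says.** Section 2.4 gives the requirement: "We estimate that we need a total sample size of 680 patients (17 practices with an average of 40 patients per practice"). The target is 80% power at a 5% alpha level for 35% versus 20% on the composite outcome, with an ICC of 0.03 and 20% loss to follow-up. No allocation ratio or test is named.

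The design sections give other numbers:

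- Summary: "Fifteen practices will be randomised to either care as usual according to the current SDM programmes" or to the new programme, and "Approximately 40 patients per practice with DM2, COPD and/or CVD will be recruited".
- Section 2: the cooperatives "will recruit 15 general practices (clusters) who will be randomized using a 2:1 ratio in two study groups".
- Section 4.2: "Practices will be randomised to intervention group (10 clusters) or comparator (5 clusters) in a 2:1 ratio". It continues: "Five additional clusters will be randomised to the control group by a 2:1 ratio randomisation procedure in the parallel cluster RCT named EMBOSS".

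Section 4.2 describes the EMBOSS comparison as one in which "at 12 months follow-up the effects will be compared to patients with low SES who have received care as usual", and adds that "Figure 2 illustrates the combined randomisation procedure of both the OPTIMA FORMA and the EMBOSS cluster RCT". That figure is not reproduced in the text available for this review.

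Sections 6 and 6.1 model an intervention-versus-control effect with a random effect for practice and do not mention EMBOSS. Section 4.7 ends the study in its current design if the necessary number of clusters is not recruited, without giving that number.

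**The concern.** The plan gives 17 practices as the requirement and 15 as the number randomised. Section 4.2 opens the way to a third total, 20. At about 40 patients per practice, 15 practices give about 600 patients against the 680 said to be needed.

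The EMBOSS sentence can be read in two ways. It may enlarge this trial's control group from 5 to 10 practices. Or it may describe EMBOSS's own control arm, whose stated comparison concerns patients with low socioeconomic status, whereas this trial's population is everyone enrolled in the disease programmes.

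Two things are at stake. If the EMBOSS controls are left out, the trial has fewer practices than its own calculation requires, and in an unequal split. If they are brought in, half the control clusters come from another trial, yet neither the power calculation nor the primary analysis says so, and the choice of which of their patients count stays open. The stopping provision in Section 4.7 also cannot be applied while its threshold could be 15, 17 or 20.

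**Working it through.** **Inputs.** From Section 2.4: 35% versus 20%, 80% power, 5% alpha, ICC 0.03, 40 recruited per practice, 20% loss. From Section 6: two-sided testing. Evaluable patients per practice: 40 × 0.8 = 32. Design effect: 1 + (32 − 1) × 0.03 = 1.93.

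**Step 1: reproduce the 680.** Let N be the total for individual randomisation. Patients to recruit = N × 1.93 / 0.8; practices = that figure / 40.

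| Ratio and variance | N | Patients | Practices |
|---|---|---|---|
| 1:1 pooled | 275.8 | 665.4 | 16.64 |
| 1:1 unpooled | 270.4 | 652.2 | 16.31 |
| 2:1 unpooled | 286.5 | 691.1 | 17.28 |
| 2:1 pooled | 316.4 | 763.2 | 19.08 |

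Both 1:1 versions round up to 17 practices, so the stated figure reproduces and equal allocation fits best. The 2:1 unpooled version is also near 680, though it rounds up to 18 practices, so the ratio is not established with certainty. A design effect based on 40 per practice (2.17) gives 733 to 858 patients, none near 680, so 32 evaluable is the reading that fits.

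**Step 2: power for each design.** With k practices in an arm, the effective size is n = k × 32 / 1.93.

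- s₁ = √(0.20 × 0.80 / n_C + 0.35 × 0.65 / n_I)
- s₀ = √(p̄(1 − p̄)(1/n_C + 1/n_I)), where p̄ is the weighted mean rate
- Unpooled power = Φ(0.15 / s₁ − 1.96)
- Pooled power = Φ((0.15 − 1.96 s₀) / s₁)

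For 10:5, n_I = 165.8, n_C = 82.9 and p̄ = 0.30. This gives s₁ = 0.0575 and s₀ = 0.0616. Unpooled: Φ(2.61 − 1.96) = 74.2%. Pooled: Φ(0.508) = 69.4%.

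| Design | n_I, n_C | Pooled | Unpooled |
|---|---|---|---|
| 17 practices, 1:1 | 140.9, 140.9 | 80.9% | 81.6% |
| 17 practices, 11:6 | 182.4, 99.5 | 76.4% | 80.1% |
| 17 practices, exact 2:1 | 187.9, 94.0 | 75.1% | 79.4% |
| 15 practices, 10:5 | 165.8, 82.9 | 69.4% | 74.2% |
| 20 practices, 10:10 | 165.8, 165.8 | 86.7% | 87.3% |

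The loss from 17 practices to 10:5 depends on what Section 2.4 assumed: 80.85 − 69.42 = 11.4 points (1:1 pooled), 81.61 − 74.23 = 7.4 (1:1 unpooled), 80.15 − 74.23 = 5.9 (11:6 unpooled) or 79.36 − 74.23 = 5.1 (exact 2:1 unpooled).

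**Step 3: detectable difference at 80% power, control rate held at 20%.** At 10:5 it is 17.1 points (pooled) or 16.1 (unpooled). At 10:10 it is 13.6 or 13.5.

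**Step 4: how many EMBOSS patients would be enough?** The documents give no number, so this is an assumption. If each of the five added practices supplies m evaluable, comparable patients, then n_C = 82.9 + 5m / (1 + (m − 1) × 0.03). Power reaches 80% at m = 9.29 (pooled) or 5.48 (unpooled), that is, 10 or 6 whole patients per practice. At m = 5 it is 76.6% or 79.6%.

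**Sensitivity.** A t reference with practices minus 2 degrees of freedom (unpooled standard error) gives 67.5% at 10:5 and 83.5% at 10:10. It also gives only 76.2% for 17 practices at 1:1, so it does not reproduce the stated 80% and the conclusion does not rely on it.

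**The case against.** The strongest reply is that the numbers answer different questions. Seventeen is a requirement, fifteen is what this trial randomises itself, and the five EMBOSS controls bring the total to 20, which exceeds 17. Section 4.2 leans that way: the sentence sits in this trial's allocation section, calls the clusters additional, assigns them to the control group, and points to a combined procedure. The 680 also reproduces best at 1:1, which agrees with 10:10 and not with 10:5. The missing figure may confirm all this. On that view the arithmetic is sound and only a clarification is needed.

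Much of this stands. The sharing reading is the more natural one, no shortfall is shown under it if the EMBOSS practices supply enough patients, and nothing can be held against the plan because a figure was lost in extraction. It is also true that 69-74% is not a floor, and that including very few EMBOSS patients would still leave power below 80%.

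The reply does not remove the inconsistency. The Summary and Section 2 still define a 15-practice trial and Section 2.4 a 17-practice one, and neither is 20. A randomisation diagram could show where the clusters come from, but it would not make those sections agree or add the missing ratio to Section 2.4. The text also does not say which EMBOSS control patients would be comparable, when that trial's comparison is confined to low socioeconomic status, or how many are expected.

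**Conclusion.** The concern holds. The only power statement describes neither design that the protocol can be read as planning, and the text does not identify the practices that form the primary control group.

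- **EMBOSS controls excluded (10:5):** power for 15 points is about 69-74%, which is 5 to 11 points below the 17-practice figure depending on the unstated ratio and formula. The detectable difference is about 16-17 points.
- **EMBOSS controls included (10:10):** power is about 87% if each of those practices supplies 40 recruited, comparable patients. It stays at or above 80% with as few as 10 (pooled) or 6 (unpooled) evaluable patients each. No shortfall is shown in that case, but Section 2.4 does not describe that design.

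These figures rest on the plan's own rates, ICC and loss to follow-up, 32 evaluable patients in every practice except where varied for EMBOSS, and a normal-approximation test. The underpowering is conditional; the disagreement between 15, 17 and 20 is not. It must be fixed, because the number of clusters and the make-up of the control group are basic to a cluster trial.

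**What to change.** 1. In Sections 4.2 and 6.1, state whether the EMBOSS control practices are in the primary comparison. If they are, say which of their patients count (all, or only those with low socioeconomic status) and how many are expected.
2. Restate Section 2.4 for that design, naming the allocation ratio and the test.
   - If excluded: 15 practices at 10:5, about 600 patients, with the 80% replaced by the recalculated power for 15 points (about 69-74% on the plan's inputs) or by the detectable difference (about 16-17 points).
   - If included: 20 practices at 10:10, with power calculated for the expected EMBOSS numbers. The 87% applies only with 40 recruited, comparable patients in each.
3. Use one practice number in the Summary and Sections 2, 2.4 and 4.2, and give the necessary number in Section 4.7.

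The cost is wording plus one recorded decision, which should be made before outcome data are seen. No extra patients or practices are asked for. The downside is that the stated power may become less favourable.
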